#### 4.4.1.2.5 Duration

Duration is derived from the start and stop dates of the unsolicited non-serious AE provided in the clinical database:

- stop date of unsolicited non-serious AE - start date of unsolicited non-serious AE + 1.

The duration should be considered as missing only if one or both of the start and stop dates of the unsolicited non-serious AE is missing or partially missing.

#### 4.4.1.3 SAEs

##### 4.4.1.3.1 Last Vaccination

Last vaccination before an SAE is derived from the last visit numbers provided in the clinical database and is calculated as follows:

- If an SAE has a non-missing visit number, the visit number should be used to determine the last vaccination before the SAE
- If the visit number is missing, then the start date should be used to determine the last vaccination before the SAE

#### 4.4.1.3.2 Time of Onset

Time of onset will be computed using the same methodology as for unsolicited non-serious AEs described in [Section 4.4.1.2.4](#).

SAEs will be analyzed throughout the study using the following periods:

- Within 30 days
- During the study (i.e., all SAEs occurred during the study)

An SAE with missing time of onset will be considered to have occurred just after the vaccination indicated by the visit number, so will be included in these tables.

Note: SAEs that occurred before vaccination (negative time of onset) will not be included in analysis, but will be listed separately.

#### 4.4.1.3.3 Duration

Duration will be computed using the same methodology as for unsolicited non-serious AEs described in [Section 4.4.1.2.5](#).

#### 4.4.1.4 Other Safety Endpoints

##### 4.4.1.4.1 Pregnancy

Not applicable for this study.

##### 4.4.1.4.2 Action Taken

This information will be summarized as collected, including missing observations. No derivation or imputation will be done.

##### 4.4.1.4.3 Seriousness

This information will be summarized as collected. No derivation or imputation will be done.

##### 4.4.1.4.4 Outcome

This information will be summarized as collected. No derivation or imputation will be done.

##### 4.4.1.4.5 Causality

This information will be summarized as collected. Missing causality (relationship) will be handled as described in [Section 5.3.1.2](#).

##### 4.4.1.4.6 AEs Leading to Study Discontinuation

A flag is available in the clinical database for all AEs in order to identify AEs leading to discontinuation.

In general, the items that are counted are:

- Disposition table: A subject who has, on the termination form, the reason for early termination “Serious Adverse Event” or “Other adverse event” checked
- Safety overview table: A subject who has either on the termination form, the reason for early termination “Serious Adverse Event” or “Other adverse event” checked or lists an AE on an AE page (solicited, unsolicited, or SAE) that has “Reaction Leading to Termination” or “Event Leading to Termination” or “Serious Adverse Event Leading to Termination” checked that is at least Grade 1 and is within the time period indicated
- System Organ Class/Preferred Term (SOC/PT) table: An event (solicited, unsolicited, or SAE) that has “Reaction Leading to Termination” or “Event Leading to Termination” or “Serious Adverse Event Leading to Termination” checked that is at least Grade 1 and is within the time period indicated

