### 9.3.2.2 Safety Endpoints

The observational endpoints for the evaluation of safety are:

- Occurrence, nature (Medical Dictionary for Regulatory Activities [MedDRA] preferred term), duration, intensity, and relationship to vaccination(s) of any unsolicited systemic AEs reported in the 30 minutes after vaccination(s).
- Occurrence, time to onset, number of days of occurrence, intensity, action taken, and whether the reaction led to early termination from the study, of solicited (prelisted in the subject's diary card and CRF) injection site reactions occurring up to 7 days after vaccination(s).
- Occurrence, time to onset, number of days of occurrence, intensity, action taken, and whether the reaction led to early termination from the study, of solicited (prelisted in the subject's diary card and CRF) systemic reactions occurring up to 7 days after vaccination(s).
- Occurrence, nature (MedDRA preferred term), time to onset, duration, intensity, action taken, relationship to vaccination (for systemic AEs only), and whether the event led to early termination from the study, of unsolicited AEs up to Visit 2 after vaccination(s).
- Occurrence, nature (MedDRA preferred term), time to onset, duration, seriousness criteria, relationship to vaccination, outcome, and whether the SAE led to early termination from the study, of SAEs throughout the trial.

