#### **4.4.1.2 Unsolicited Non-serious AEs**

##### **4.4.1.2.1 Presence**

An observation will be considered an event if it has at least a verbatim term and is not a Grade 0 intensity event. Grade 0 events should be included in the listing “Unsolicited non-serious adverse events not included in the safety analysis.”

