##### *Safety*

For this trial, the safety data will be assessed by applying descriptive statistical methods, supplemented by the calculation of CIs to aid interpretation. The exact binomial distribution (Clopper-Pearson method) for proportions will be used in the calculation of the 95% CIs of events. Analysis tables and listings will contain at least the descriptions listed in Table 5.2

Table 5.2: Statistical analyses for safety observational objectives

Safety Events	Time and Group	Description
Immediate unsolicited systemic AE	Within 30 minutes after injection for all subjects in Groups 1 to 12 at D0	Proportion of subjects that have the event, MedDRA terms, intensity, relationship to vaccine, study discontinuation
Solicited injection site reactions	Up to 7 days after D0 for all subjects in Groups 1 to 12	Proportion of subjects that have the event, onset, duration, intensity, action taken, study discontinuation, temperature collection routes
Solicited systemic reactions	Up to 7 days after D0 for all subjects in Groups 1 to 12	Proportion of subjects that have the event, onset, duration, intensity, action taken, study discontinuation
Unsolicited AE	Up to 30 days after D0 for all subjects in Groups 1 to 12	Proportion of subjects that have the event, MedDRA terms, onset, duration, intensity, relationship, action taken, study discontinuation
SAE	From Visit 1 to Visit 2 for all subjects in Groups 1 to 12	Proportion of subjects that have the event, MedDRA terms, onset, duration, relationship, seriousness criteria, outcome, study discontinuation

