#### 5.3.1.4 Intensity

For solicited reactions, missing intensities will be handled as described in [Section 4.4.1.1.1](#). For unsolicited non-serious AEs, missing intensities will remain missing and will not be imputed.

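### Read literally, the at-least-Grade-1 condition in SAP 4.4.1.4.6 leaves ungraded SAEs and unsolicited AEs with missing intensity out of the SOC/PT discontinuation table

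*SAP*

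**What the plan says.** SAP 4.4.1.4.6 sets three counting rules for discontinuation.

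- **Disposition table:** the child counts if the termination form gives an SAE or another AE as the reason.
- **Safety overview table:** there are two routes. One is the termination form ("A subject who has either on the termination form, the reason for early termination"). The other is a flagged event on an AE page, subject to grade and period.
- **SOC/PT table:** only the event route exists. The rule begins "System Organ Class/Preferred Term (SOC/PT) table: An event (solicited, unsolicited, or SAE) that has" and, after naming the three flags, ends "checked that is at least Grade 1 and is within the time period indicated".

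On SAE attributes, the protocol endpoint (9.3.2.2) lists occurrence and nature, then "time to onset, duration, seriousness criteria, relationship to vaccination, outcome, and whether the SAE led to early termination from the study". The SAE row of SAP Table 5.2 reads "Proportion of subjects that have the event, MedDRA terms, onset, duration, relationship, seriousness criteria, outcome, study discontinuation". Neither includes intensity.

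On unsolicited non-serious AEs, SAP 5.3.1.4 states: "For unsolicited non-serious AEs, missing intensities will remain missing and will not be imputed". SAP 4.4.1.2.1 states: "An observation will be considered an event if it has at least a verbatim term and is not a Grade 0 intensity event".

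**The concern.** The grade condition is written to cover SAEs, which the rule names both as an event type and through their own flag. A condition on grade can only be met by an event that has one. If an SAE carries no grade, or the grade of an unsolicited AE is missing, the event fails the test although it is real, flagged and inside the period.

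Whether an SAE ended participation is a named part of the protocol's SAE endpoint. A reader of the report could see a withdrawal for an SAE in the disposition table and find no matching term in the table meant to explain it. The rule also departs from the SAP's practice elsewhere of resolving missing safety attributes inclusively: missing causality is treated as related (5.3.1.2), and events with missing onset stay in the tables (4.4.1.2.4, 4.4.1.3.2).

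**Working it through.** The plan states no figure on this point, so the check is a trace of the rule.

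**Step 1. Where is a grade specified?**

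- *Solicited reactions:* yes (Protocol Tables 9.1 and 9.2; SAP 4.4.1.1.1).
- *Unsolicited non-serious AEs:* yes (Protocol 9.3.2.3.3; SAP 4.4.1.2.2), with Missing as an allowed category.
- *SAEs:* no SAE-specific section gives one. It is absent from the SAE endpoint (Protocol 9.3.2.2), the SAE assessment section (9.3.2.3.4) and SAP 4.4.1.3, which derives last vaccination, onset and duration only. In SAP Table 5.2 every row lists intensity except the SAE row. Seriousness cannot stand in for a grade, because Protocol 9.3.2.1 separates serious from severe.

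**Step 2. Apply the three rules to a child whose event is flagged and in period.**

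| Record | Disposition | Overview | SOC/PT |
|---|---|---|---|
| SAE without grade; termination form gives SAE | counted | counted, by the form | not counted |
| Unsolicited non-serious AE, intensity missing; form gives other AE | counted | counted, by the form | not counted |
| Either event flagged, but form gives a non-AE reason | not counted | not counted | not counted |
| Solicited reaction, intensity missing; form gives other AE | counted | counted, by the form | not counted |

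**Step 3. Compare with the rest of the SAP.**

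- Row 1 sits badly with the SAE row of Table 5.2, which plans study discontinuation for SAEs with no grade condition.
- Row 2 conflicts with SAP 4.4.1.2.1. That section removes only Grade 0, so an AE with a missing grade is an event there but not in the discontinuation table.
- Row 3 requires the event flag and the termination form to disagree.
- Row 4 is consistent with SAP 4.4.1.1.3, where presence of a solicited reaction requires Grade 1, 2 or 3 and missing intensity means missing presence. It needs no change.

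**Step 4. Size.** If k events fall in rows 1 and 2, the disposition and overview tables reflect k and the SOC/PT table shows 0, a shortfall of k − 0 = k. For illustration only, with assumed counts in a group of 200: 1/200 = 0.5% and 2/200 = 1.0%, against 0 tabulated. The documents give no expected count. Protocol 1.2.2 reports no discontinuations for AEs or SAEs in MET32, MET44 or MET54, which points to a k near zero.

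**The case against.** The strongest reply is that the literal reading defeats the rule's purpose. A rule that names SAEs and their flag cannot have been meant to exclude them. The aim was presumably to drop Grade 0 events, and the rules are introduced as general ones. A sensible programmer would probably keep SAEs. That limits the practical risk, but the text does not say so, and the gap for missing intensity needs no assumption about intent.

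A reader might go further and infer that SAEs are never graded, so that every SAE discontinuation is lost. The documents do not support that. Absence of a grade is inferred from consistent omission, and the case report form is not available. Protocol 9.3.2.1 defines unsolicited non-serious AEs by excluding SAEs from unsolicited AEs, so the wider class includes SAEs. The unsolicited and immediate AE endpoints in 9.3.2.2 list intensity without restricting it to non-serious events. The solicited-reaction action scale in 9.3.2.3.2 includes inpatient hospitalization, so a serious solicited reaction may carry a grade.

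Nor is the endpoint lost. The SAE row of Table 5.2 separately plans MedDRA terms and study discontinuation, and the SAE itself is tabulated regardless.

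It is also tempting to say that a child could be missed in all three tables. The third row of the trace shows how, but it needs contradictory records. Protocol 5.2.9 has safety-driven withdrawals recorded as SAE or other AE, 5.2.11 ranks SAE first among reasons for termination, and 11.2 provides consistency checks, queries and SAE reconciliation. It would be a data error, not an expected outcome.

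Finally, all vaccine is given on Day 0, so discontinuation here means leaving follow-up, not stopping treatment.

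**Conclusion.** The point holds as a minor drafting fault. Followed literally, SAP 4.4.1.4.6 drops an ungraded SAE, or an unsolicited non-serious AE with missing intensity, from the SOC/PT discontinuation table while the termination form places the same child in the disposition and overview tables. The SAE part assumes that no grade is recorded for the event, which the documents suggest but do not state. The missing-intensity part rests on SAP text alone. The shortfall is one tabulated event for each event affected, probably few or none, in a descriptive safety table. No hypothesis test or immunogenicity result is affected.

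**What to change.** Amend SAP 4.4.1.4.6 for the event route of the overview table and for the SOC/PT table:

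- **SAEs:** count every in-period SAE flagged as leading to termination, regardless of grade.
- **Unsolicited non-serious AEs:** replace *at least Grade 1* with *not Grade 0*, to match SAP 4.4.1.2.1.
- **Solicited reactions:** keep *at least Grade 1*, to match SAP 4.4.1.1.3. Extending *not Grade 0* to them would count reactions that the SAP does not treat as present.

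If the case report form does record a grade for SAEs, the SAP should say where it comes from; the proposed SAE rule works either way. The cost is a few words in the SAP and the matching program condition, with no new data. The tabulated discontinuation count may become slightly less favourable.

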#### 4.4.2 Immunogenicity

##### 4.4.2.1 Computed Values for Analysis

In order to appropriately manage extreme values (< the lower limit of quantitation [LLOQ] and  $\geq$  the upper limit of quantitation [ULOQ]) for analysis purposes, the following computational rule is applied to the values provided in the clinical database for each BL drawn:

- If a value is < LLOQ, then use the computed value LLOQ/2
- If a value is between  $\geq$  LLOQ and < ULOQ, then use the value
- If a value is  $\geq$  ULOQ, then use the computed value ULOQ

##### 4.4.2.2 Fold-rise

The derived endpoint fold-rise is driven by both baseline and post-baseline computed values and is computed as follows:

- Calculate the fold-rise of values as the ratio of post-baseline computed value divided by baseline computed value

Note: If baseline or post-baseline is missing, then fold-rise is missing.

##### 4.4.2.3 Vaccine response

Vaccine response for PT and FHA antigens:

- If the pre-vaccination concentration is  $\geq 4 \times$  LLOQ, then the post-vaccination concentration is  $\geq 2 \times$  the pre-vaccination concentration
- If the pre-vaccination concentration is <  $4 \times$  LLOQ, then the post-vaccination concentration is  $\geq 4 \times$  the pre-vaccination concentration

Then the derived vaccine response rates indicator will be “Yes” for that test, otherwise vaccine response rates will be “No”.

#### **4.4.2.4 Vaccine Seroresponse of hSBA**

The derived seroresponse indicator for hSBA will be “Yes” if

- hSBA titer is  $< 1:8$  at baseline with a post-baseline hSBA titer  $\geq 1:16$
- or hSBA titer is  $\geq 1:8$  at baseline with a  $\geq 4$ -fold increase at post-baseline

#### **4.4.2.5 Vaccine Seroresponse of rSBA**

The derived seroresponse indicator for rSBA will be “Yes” if

- rSBA titer is  $< 1:8$  at baseline with a post-baseline rSBA titer  $\geq 1:32$
- or rSBA titer is  $\geq 1:8$  at baseline with a  $\geq 4$ -fold increase at post-baseline

#### **4.4.2.6 Efficacy**

Not applicable

### **4.4.3 Derived Other Variables**

#### **4.4.3.1 Age for Demographics**

The age of a subject in the study was the calendar age in months at the time of inclusion.

#### **4.4.3.2 Duration of a Subject in the Trial**

The duration of a subject in the study is computed as follows:

Maximum (date of last visit, date of termination) – (date of Visit 1 of that subject) +1.

#### **4.4.3.3 Duration of the Study**

The duration of the study is computed as follows:

Maximum of all subjects (date of last visit, date of termination) – Minimum of all subjects (date of Visit 1) + 1.

## **5 Statistical Methods and Determination of Sample Size**

The statistical analyses will be performed under the responsibility of the Sponsor’s Biostatistics platform using SAS® Version 9.4 software or later.

The results of the statistical analysis will be available in the final clinical study report. For descriptive purposes, the following statistics will be presented:

**Table 5.1: Descriptive statistics produced**

Baseline characteristics and follow-up description	Categorical data	Number of subjects. Percentage of subjects.
	Continuous data	Mean, standard deviation, quartiles, minimum, and maximum.
Clinical safety results	Categorical data	Solicited: Number and percentage (95% CIs) of subjects. Unsolicited: Number and percentage (95% CIs) of subjects, and number of events.
Immunogenicity results	Categorical data (seroresponse, <math>\geq 4</math> fold rise, cutoff)	Number and percentage (95% CIs) of subjects.
	Continuous data (titer / concentration)	$\text{Log}_{10}$ : Mean and standard deviation. $\text{Anti-Log}_{10}$ (work on $\text{Log}_{10}$ distribution, and $\text{anti-Log}_{10}$ applied): Geometric mean (GM), 95% CI of the GM. Graphical representation by Reverse Cumulative Distribution Curve (RCDC).

The confidence interval (CI) for the single proportion will be calculated using the exact binomial method (Clopper-Pearson method, quoted by Newcombe (1)). For immunogenicity results, assuming that  $\text{Log}_{10}$  transformation of the titers follows a normal distribution, at first, the mean and the 95% CI will be calculated on  $\text{Log}_{10}$  (titers) using the usual calculation for normal distribution (using Student's t distribution with n-1 degree of freedom), then antilog transformations will be applied to the results of calculations, in order to provide GMs and their 95% CI.

## 5.1 Statistical Methods

### 5.1.1 Hypotheses and Statistical Methods for Primary Objectives

No hypotheses will be tested. Descriptive statistics will be presented by group and by pooled group for subjects included in South Korea and Thailand (Groups 1 & 10 pooled, Groups 2 & 11 pooled, and Groups 3 & 12 pooled).

#### 5.1.1.1 Statistical Methods

Ab titers against meningococcal serogroups A, C, Y, and W measured by hSBA before and 30 days after vaccination with MenACYW conjugate vaccine will be described by:

- GMT and 95% CI
- Titer distribution and reverse cumulative distribution curves (RCDCs)
- Percentage of subjects with titer  $\geq 1:4$  and  $\geq 1:8$  and 95% CI

- Percentage of subjects with titer  $\geq$  4-fold rise from pre-vaccination to post-vaccination, and 95% CI
- Percentage of subjects with hSBA vaccine seroresponse defined as follows:
  - For a subject with a pre-vaccination titer  $<$  1:8, the post-vaccination titer must be  $\geq$  1:16
  - For a subject with a pre-vaccination titer  $\geq$  1:8, the post-vaccination titer must be at least 4-fold greater than the pre-vaccination titer

### **5.1.2 Hypotheses and Statistical Methods for Secondary Objectives**

No hypotheses will be tested. Descriptive statistics will be presented.

#### **5.1.2.1 Statistical Methods**

The analyses on the concomitant vaccines will include GMT and titer distribution or GMC, and RCDC, as well as % of subjects with:

- Abs to the antigens contained in MMR vaccine measured before and 30 days after vaccination with MMR vaccine:
  - anti-measles Ab concentrations  $\geq$  255 mIU/mL
  - anti-mumps Ab concentrations  $\geq$  10 Mumps Ab units/mL
  - anti-rubella Ab concentrations  $\geq$  10 IU/mL
- Anti-varicella Ab concentrations before and 30 days (+14 days) after vaccination with V vaccine  $\geq$  5 gpELISA Ab units/mL

- Abs to the antigens contained in DTaP-IPV-HB-Hib vaccine measured before and 30 days after vaccination with DTaP-IPV-HB-Hib vaccine:
  - anti-tetanus Ab concentrations  $\geq 0.01$  and 0.1 IU/mL at D0 and  $\geq 0.1$  and 1.0 IU/mL at D30
  - anti-pertussis (PT, and FHA) Ab concentrations and pertussis vaccine response

---

 Pertussis vaccine response:

- If the pre-vaccination concentration is  $< 4 \times$  LLOQ, then the post-vaccination concentration is  $\geq 4 \times$  pre-vaccination concentration;
- If the pre-vaccination concentration is  $\geq 4 \times$  LLOQ, then the post-vaccination concentration is  $\geq 2 \times$  the pre-vaccination concentration.

- Abs to the antigens contained in DTaP-IPV-HB-Hib vaccine measured 30 days after vaccination with DTaP-IPV-HB-Hib vaccine:
  - anti-diphtheria Ab concentrations  $\geq 0.1$  and 1.0 international Units (IU)/mL
  - anti-PRP Ab concentrations and  $\geq 0.15$  and 1.0  $\mu\text{g}/\text{mL}$
  - anti-poliovirus types 1, 2, and 3 Ab titers  $\geq 1:8$
  - anti-hepatitis B surface antigen Ab concentrations  $\geq 10$  mIU/mL,  $\geq 100$  mIU/mL
- Anti-pneumococcal Ab concentrations  $\geq 0.35$   $\mu\text{g}/\text{mL}$  and 1.0  $\mu\text{g}/\text{mL}$  and 95% CI for serotypes 1, 3, 4, 5, 6A, 6B, 7F, 9V, 14, 18C, 19A, 19F, and 23F measured before and 30 days after vaccination with PCV13 vaccine

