### 5.2.5 Exclusion Criteria

An individual fulfilling *any* of the following criteria is to be excluded from trial enrollment:

- 1) Participation in the 4 weeks preceding the first trial vaccination or planned participation during the present trial period in another clinical trial investigating a vaccine, drug, medical device, or medical procedure
- 2) Receipt of any vaccine in the 4 weeks (28 days) preceding the first trial vaccination or planned receipt of any vaccine prior to Visit 2 except for influenza vaccination, which may be received at least 2 weeks before or after the study investigational vaccines. This exception includes monovalent pandemic influenza vaccines and multivalent influenza vaccines.
- 3) Previous vaccination against meningococcal disease with either the trial vaccine or another vaccine (i.e., mono- or polyvalent, polysaccharide, or conjugate meningococcal vaccine containing serogroups A, C, Y, or W; or meningococcal B vaccine)
- 4) **For subjects enrolled at sites in the Russian Federation:** previous vaccination with the third dose of PCV13 in subjects 15 to 23 months of age (eligible for Group 7 or 9)
- 5) **For subjects enrolled at sites in Mexico:** known history of seizures, or uncontrolled neurologic disorder (including epilepsy); or encephalopathy of unknown etiology occurring within 7 days following previous vaccination with pertussis containing vaccine; previous vaccination with DTaP-IPV-HB-Hib or DTaP-containing vaccine at 12 to 23 months of age.
- 6) **For subjects enrolled at sites in South Korea and Thailand:** known history of seizures, cerebral injury, or encephalopathy; previous vaccination with MMR or V at or before 12 to 23 months of age.
- 7) Receipt of immune globulins, blood or blood-derived products in the past 3 months
- 8) Known or suspected congenital or acquired immunodeficiency; or receipt of immunosuppressive therapy, such as anti-cancer chemotherapy or radiation therapy, within the preceding 6 months; or long-term systemic corticosteroid therapy (prednisone or equivalent for more than 2 consecutive weeks within the past 3 months)
- 9) History of meningococcal infection, confirmed either clinically, serologically, or microbiologically
- 10) At high risk for meningococcal infection during the trial, according to the Investigator's judgment (specifically, but not limited to, subjects with persistent complement deficiency,

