#### ***Anti-Varicella Antibodies***

The assay for measuring anti-varicella antibodies will be performed by Merck, Richmond, VA, USA.

The glycoprotein enzyme-linked immunosorbent assay (gpELISA) detects antibodies to varicella zoster virus (VZV). The assay detects antibodies to VZV glycoprotein (gp), which have been purified from MRC-5 cells infected with the KMcC strain of VZV by lectin affinity chromatography. The reactivity of the sera to the gp antigens from uninfected MRC-5 cells (denoted as TCC wells) is subtracted from the reactivity of the sera to the gp antigens purified from VZV-infected MRC-5 cells. The concentration of serum antibody to the VZV gp antigen as determined by gpELISA is shown to correlate with neutralizing antibody concentrations. The assay uses the “second antibody” format with varicella glycoprotein (gp) antigen and MRC-5 TCC glycoprotein coated on the solid phase microtiter plate. Diluted sera are dispensed into 2 VZV gp antigen coated wells and 2 MRC5 gp coated wells for each standard curve point, control, and sample. Antibody to the varicella virus in a test sample binds to the antigen coated plate. Antibody to varicella glycoprotein in a test sample, bound to the antigen on the solid phase microtiter plate, is subsequently detected using goat anti-human IgG alkaline phosphatase conjugate. After substrate addition for color development, quantitation is obtained by comparison of sample DOD to a standard curve. The DOD is determined by subtracting the average OD of the TCC coated wells from its corresponding VZV gp average OD. Results for the assay are reported as concentration of antibody in gpELISA units/mL. The serostatus cutoff for the varicella assay is 1.25 gpELISA Ab units/mL.

These anti-measles, mumps, rubella, and varicella methods will be performed on BL1 and BL2 samples collected from Groups 1, 3, 10, and 12 only.

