### 12.3.2 Immunogenicity

Missing immunogenicity data will not be imputed. All subjects in the appropriate population with valid immunogenicity data will be included in the immunogenicity analyses. No test or search for outliers will be performed.

In order to appropriately manage extreme values (undetectable responses < LLOQ and  $\geq$  upper limit of quantitation [ULOQ]), the following computational rule is applied to the values provided in the clinical database for each blood sample drawn for analysis purposes:

- If a value is < LLOQ, then use the computed value LLOQ/2
- If a value is between  $\geq$  LLOQ and < ULOQ, then use the value
- If a value is  $\geq$  ULOQ, then use the computed value ULOQ

The derived endpoint of fold-rise is computed as follows:

- Calculate the fold-rise of values as the ratio of post-baseline computed value divided by baseline computed value

If baseline or post baseline value is missing, then the seroconversion is missing.

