#### 5.7 Changes in the Conduct of the Trial or Planned Analyses

The SAP core V1.0 was updated to version 2.0 to reflect the changes following amendment 3 of the protocol (version 4.0 dated 11Sep2017; inclusion of study groups in Thailand).

Moreover, for MMRV antigens and in order to reflect the assay used for analysis, the respective thresholds to be considered as clinical endpoint were changed as below:

- anti-measles Ab concentrations  $\geq$  255 mIU/mL
- anti-mumps Ab concentrations  $\geq$  10 Mumps Ab units/mL
- anti-rubella Ab concentrations  $\geq$  10 IU/mL
- anti-rubella Ab concentrations  $\geq$  5 gpELISA Ab units/mL

Definition of vaccine response for PT and FHA antigens was modified as follow:

- If the pre-vaccination concentration is  $\geq$  4 x LLOQ, then the post-vaccination concentration is  $\geq$  2 x the pre-vaccination concentration

- If the pre-vaccination concentration is  $< 4 \times \text{LLOQ}$ , then the post-vaccination concentration is  $\geq 4 \times$  the pre-vaccination concentration

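### MMR and varicella results are summarised only in all per-protocol children, so the Day 30 percentages mix vaccine take with antibody already present at baseline; a summary in baseline-seronegative children should be added

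*SAP*

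**What the plan says.** SAP 5.1.2.1 introduces the secondary outputs with "The analyses on the concomitant vaccines will include GMT and titer distribution or GMC, and RCDC, as well as % of subjects with", followed by one threshold or more per antigen. For this vaccine pair the item is "Abs to the antigens contained in MMR vaccine measured before and 30 days after vaccination with MMR vaccine". The thresholds are measles 255 mIU/mL, mumps 10 units/mL, rubella 10 IU/mL and varicella 5 gpELISA units/mL. SAP 5.7 explains that "the respective thresholds to be considered as clinical endpoint were changed as below". SAP 5.2.4 places these analyses on the PPAS, with the Full Analysis Set as exploratory. Neither set depends on baseline serostatus.

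A response that depends on the baseline value is defined elsewhere in the SAP: section 4.4.2.3 ("Vaccine response for PT and FHA antigens"), section 4.4.2.4 ("The derived seroresponse indicator for hSBA will be" Yes under stated baseline and post-baseline conditions) and section 4.4.2.5 for rSBA. No such definition exists for measles, mumps, rubella or varicella. SAP 4.4.2.2 gives a general fold-rise formula, but 5.1.2.1 does not apply it to these antigens.

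Eligibility in South Korea and Thailand bars previous MMR or varicella vaccination (Protocol 5.2.4, and 5.2.5 criterion 6). The only infection history that excludes a child is criterion 9, "History of meningococcal infection, confirmed either clinically, serologically, or microbiologically".

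Baseline data will exist. Protocol 9.2.1.2 says of the four viral assays that these "methods will be performed on BL1 and BL2 samples collected from Groups 1, 3, 10, and 12 only". The protocol also gives a serostatus cutoff for each assay: measles 120 mIU/mL, mumps 10 units/mL, rubella 10 IU/mL and varicella 1.25 gpELISA units/mL.

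**The concern.** The children are to be unvaccinated against these four viruses, but they need not be free of antibody or past disease, and they may be up to 23 months old. A child who is already above a threshold on Day 0 and remains there appears on Day 30 exactly like a child whom the vaccine converted.

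Protocol 1.4 and SAP 1 state that the trial should show that routine toddler vaccines are not affected by giving MenACYW at the same visit. For a first dose of live vaccine, the most direct measure of that is the response among children who were seronegative when vaccinated. The planned summaries approach this only indirectly. Separate Day 0 and Day 30 percentages give the conversion rate only if every baseline-positive child is assumed to stay above the threshold. The Day 30 GMC in seronegative children cannot be recovered from the all-children GMC.

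**Working it through.** There is no stated figure to reproduce: SAP 5.1.2 tests no hypothesis, and the sample-size section is redacted. The check is therefore an illustration.

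**Inputs from SAP 3.2.** MenACYW + MMR + V: 100 (Group 1) + 100 (Group 10) = 200. MMR + V alone: 50 (Group 3) + 50 (Group 12) = 100.

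**Assumptions, not in the documents.** The baseline-positive share p is the same in both groups. Baseline-positive children stay above the threshold. True take among the other children is r = 80% with MenACYW and 90% alone, a 10-point loss.

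**Formulas.** Day 30 percentage in all children = p + (1 − p)r. Excess over true take = p(1 − r). Difference between groups = (1 − p) × 10 points.

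| p | With MenACYW | Alone | Difference shown |
|---|---|---|---|
| 0% | 80.0 | 90.0 | 10.0 |
| 5% | 81.0 | 90.5 | 9.5 |
| 10% | 82.0 | 91.0 | 9.0 |
| 15% | 83.0 | 91.5 | 8.5 |
| 30% | 86.0 | 93.0 | 7.0 |

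At p = 10% the planned percentages exceed true take by 0.10 × 0.20 = 2.0 points and 0.10 × 0.10 = 1.0 point.

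**Does restricting to seronegative children make a loss easier to see?** At p = 10%:

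- All children: SE = √(0.82 × 0.18/200 + 0.91 × 0.09/100) = 3.95 points; 9.0/3.95 = 2.28.
- Seronegative children (180 and 90): SE = √(0.80 × 0.20/180 + 0.90 × 0.10/90) = 4.35 points; 10.0/4.35 = 2.30.

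At p = 15% the two ratios are 2.21 and 2.24. The larger difference is almost exactly offset by the smaller denominator. What is gained is an estimate of the right quantity, not sensitivity.

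**Cost in precision at p = 10% (Clopper-Pearson 95% CI).**

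- With MenACYW: 164/200 gives 76.0% to 87.1%; 144/180 gives 73.4% to 85.6%.
- Alone: 91/100 gives 83.6% to 95.8%; 81/90 gives 81.9% to 95.3%.
- Interval width rises from 11.1 to 12.2 points and from 12.2 to 13.5 points.

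**Which boundary.** For mumps and rubella the protocol cutoff and the SAP threshold have the same value. For measles (120 against 255) and varicella (1.25 against 5) they differ. The p that dilutes the planned percentage is the share above the SAP threshold. A restriction at the serostatus cutoff also removes children between the two values, so the share removed is at least p. The single p used above is exact only where the two values coincide.

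**The case against.** The strongest reply is that little is hidden and little is lost. The same percentage, GMC and RCDC are reported on Day 0, so a reader can see how many children in each group started above the threshold. The analysis is descriptive, so no error rate or power figure changes. The dilution is 0.5 to 1.5 points at p of 5% to 15%, against a standard error of about 4 points. For measles and varicella the SAP threshold lies above the serostatus cutoff, so a child with low baseline antibody must still rise to be counted. Criterion 7 of Protocol 5.2.5 also excludes children given immune globulins or blood products in the past 3 months. All of this stands, and it makes the point a modest one.

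It can also be said that tetanus and the pneumococcal serotypes have baseline results and are summarised in the same way, so MMR and varicella are not singled out. That is correct. But those are further doses in children already primed (Protocol 5.2.4), where a seronegative subset says less. MMR and varicella are first doses.

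Three stronger readings are tempting, and the documents do not support them:

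- *A reader might infer that the SAP classes already-immune children as vaccine responders.* It uses no such term for these antigens; it counts children at or above a threshold.
- *A reader might infer a bias towards showing no interference, or sizeable shifts in GMC ratios.* Allocation is randomised within South Korea and within Thailand, so baseline positives should be balanced on average. Chance imbalance is ordinary sampling variation, and SAP 5.1.2.1 lists no GMC ratio. Any figure for such a shift would need an assumed antibody gap that the documents do not supply.
- *A reader might take the sentence "If baseline or post baseline value is missing, then the seroconversion is missing" in Protocol 12.3.2 as a sign of a planned seroconversion endpoint that was then left out.* It follows the fold-rise rule, and SAP 4.4.2.2 restates it for fold-rise, so loose wording is the likelier explanation.

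**Conclusion.** The point holds as a cheap improvement to a descriptive analysis. The planned Day 30 percentages for measles, mumps, rubella and varicella overstate vaccine take in both groups by p(1 − r) and shrink any difference between groups by 1 − p. For an assumed p of 5% to 15%, a true 10-point loss shows as 9.5 to 8.5 points; at 30% it shows as 7.0. These sizes rest on an equal p in both groups, on baseline-positive children staying above the threshold, and on illustrative response rates. Because the documents do not give p, the actual effect could be negligible.

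No directional bias is expected, and the ability to detect a loss hardly changes. The reason to act is that take in seronegative children answers the stated question about interference more directly, and it cannot be recovered from the planned summaries without further assumptions.

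**What to change.** In SAP 4.4.2 and 5.1.2.1, define and report for each of the four antigens, among children below the protocol serostatus cutoff at baseline (measles 120 mIU/mL, mumps 10 units/mL, rubella 10 IU/mL, varicella 1.25 gpELISA units/mL):

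- the percentage at or above the SAP threshold on Day 30, with a Clopper-Pearson 95% CI; and
- the Day 30 GMC with its 95% CI.

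Report both by group and for Groups 1 + 10 and Groups 3 + 12 pooled. State the pooling in SAP 5.1.2, which does not mention it although 5.1.1 and 5.1.3 do. Keep the all-children outputs alongside. In the same edit, correct the last threshold in SAP 5.7, which assigns 5 gpELISA units/mL to rubella where 5.1.2.1 assigns it to varicella.

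The cost is one definition and one extra set of tables from samples and assays already planned. The price is a somewhat smaller denominator and slightly wider intervals. Eligibility does not need to change.
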